**Table 2: Study Measures/Events**

Study Week	-1	0	1	3	5	7	9	12	18	24
Session Name	Intake	Pre-Quit	TQD	W3	W5	W7	W9	W12	W18	W24
TREATMENT										
Varenicline/Placebo		X	X	X	X	X	X	X	X	
Counseling		X	X	X	X	X	X			
SCREENING/COVARIATES										
Urine Pregnancy Screen	X									
Breath Alcohol Concentration	X									
Blood Pressure	X	X	X	X	X	X	X	X	X	X
Depression/Anxiety (HADS)	X	X	X	X	X	X	X	X	X	X
Demographics	X									
Smoking History/FTND	X									
ETOH History	X									
Medical History	X									
Psychiatric History (MINI)	X		X g							
Adherence to Antiretrovirals Instrument		X			X		X	X	X	X
Pharmacy Refill Data		X d			X d			X c		X c
Concomitant Medications	X	X	X	X	X	X	X	X	X	X
Creatinine Clearance	X a									
Viral Load Assessment								X e		
Nicotine Metabolite Ratio	X									
Genetic Polymorphisms	X									
Bipolar Disorder Symptoms (MADRS f , YMRS, Additional Screener, MINI) g	X		X	X	X	X	X	X	X	X
MEDIATING VARIABLES										
Affect (PANAS)		X	X	X		X		X		
Cognitive Function (N-back, CPT)		X	X	X				X		
Nicotine Withdrawal (MNWS-W)		X	X	X		X		X		
Smoking Urges (QSU-B)		X	X	X		X		X		
TREATMENT VARIABLES										
Adherence (Pill Count)			X	X	X	X	X	X		
Adherence (Blood)				X i				X i		
Side Effects Checklist (SEC)		X	X	X	X	X	X	X	X	X
Side Effects (Open-Ended)			X	X	X	X	X	X	X	X
Suicidality (C-SSRS)	X	X	X	X	X	X	X	X	X	X
OUTCOMES										
Carbon Monoxide (CO) Test	X	X	X	X	X	X	X	X	X	X
Smoking Rate (TLFB)		X	X	X	X	X	X	X	X	X
Urine Cotinine								X b	X b	X b
Quality of Life (HAT-QoL)		X	X	X	X	X	X	X	X	X
ACASI-SHQ h				X		X		X		
HVTN Social Impact Assessment h				X		X		X		
Client Evaluation Form h								X		

\*TQD = Target Quit Day

\*W= Week

\*Note: Target Quit Day visit may occur +3 days from target date; Week 3, 5, 7, 9, 12, 18, and 24 visits may occur +/- 1 week from target date.

a Will only be completed on initially eligible participants who have not had this test within last 6 months.

b Will only be completed on participants who self-report abstinence for  $\geq$  7 days prior to the assessment.

**Version 19: February 13, 2018**

Template Version: 7 May 2008

c Participant's pharmacy will be contacted to collect pharmacy refill data.

d Collection of pharmacy contact information only.

e A viral load assessment, conducted as part of routine clinical care any time between Week 6 and Week 18, will be ascertained through medical record review or contact with health clinic and recorded.

f MADRS administered at Intake only.

g Abbreviated MINI (Major Depressive Episode-Current & Psychotic Disorder modules) only administered if a diagnosis of bipolar disorder is self-reported at Initial Eligibility Screen or Intake, or revealed via the MINI at Intake.

h Participants whose Week 3 sessions fall after the approval date for these measures will not complete them. After 50 participants have completed the questionnaire sequence, the measures will no longer be administered. If a participant misses a session, he/she will be eligible to complete the questionnaires and receive compensation at the subsequent session. All participants who complete the assessments will receive compensation.

i Blood draw will not be completed if participant has not taken study medication for 14+ days

## **Screening/Covariate Measures.**

### Urine Pregnancy Screen

The urine pregnancy screen will assess for current pregnancy in all women and will be administered at the Intake Session.

### Breath Alcohol Concentration/ETOH History

The breath alcohol concentration (BrAC) assessment will be administered at the Intake Session. The breath alcohol monitor assesses expired breath for alcohol content. Any reading >0.000 indicates alcohol consumption within the last 14 hours. The ETOH history form will be administered at the Intake Session visit and will ask subjects about their alcohol consumption over the past seven days.

### Blood Pressure

Participants presenting at intake with a blood pressure reading above 160 mmHg systolic and/or 100 mmHg diastolic will be ineligible for the study. Participants presenting with an elevated blood pressure reading between 150-160 mmHg systolic and/or 90-100 mmHg diastolic at intake will have a second blood pressure reading taken after a ten minute period in which the participants will be instructed to sit comfortably. If, after the second reading:

- A participant has a blood pressure between 150-160 mmHg systolic and/or between 90-100 mmHg diastolic, the medical staff will evaluate the situation and the participant may be deemed ineligible for the study.
- A participant has a blood pressure reading above 160 mmHg systolic and/or 100 mmHg diastolic, s/he will be ineligible for the study.

Blood pressure will be measured at each study visit. If participants present with elevated blood pressure (above 160 mmHg systolic and/or 100 mmHg diastolic) at any visit following the Intake Session, the study physician will be notified to determine how to proceed. If the elevated blood pressure reading occurs during a medication distribution visit (Pre-Quit, Week 3 or Week 7), no medication may be distributed until the study physician is contacted to evaluate the situation. A record of this evaluation will be recorded and sent to the study physician by email and will be stored in the participant's chart.

### Demographic and Smoking History

We will collect demographic (e.g., age, gender, race) and smoking history (e.g., age at initiation, past use of nicotine treatments, current rate, menthol vs. regular tobacco) data. The Fagerstrom Test for Nicotine Dependence, a validated 6-item measure of nicotine dependence, will be administered (Heatherton et al., 1991).

### Medical History

A medical history will be conducted at the Intake Session to review for any contraindications listed previously. The medical history will be completed by a research staff member. Duration since HIV/AIDS diagnosis, mode

of transmission, and viral load and CD4+ counts will be assessed. Current medication usage will be tracked at each time-point.

#### Psychiatric History

Current and lifetime prevalence of major depression, suicidality, bipolar disorder, substance abuse or dependence, psychosis, and generalized anxiety disorder will be determined using the Mini International Neuropsychiatric Interview (MINI). The MINI (Sheehan, Lecrubier et al. 1998) is a 10-15 minute structured interview developed by the World Health Organization to assess major DSM-IV Axis 1 psychiatric diagnoses. This instrument, completed by a research staff member at the Intake Session, permits both current (past 30 days) and lifetime assessments of psychiatric illness and data support its reliability and validity (Sheehan, Lecrubier et al. 1998). Suicidality will be further assessed at each visit through the Columbia Suicide Severity Rating Scale ([www.cssrs.columbia.edu](http://www.cssrs.columbia.edu)).

#### Creatinine Clearance and Liver Function

Initially eligible participants who have not had tests of creatinine clearance within the past 6 months (as determined by medical record review or provision of lab results to study staff) will have this test completed during the Intake Visit.

Estimated Creatinine Clearance (or eCrCL) will be calculated through the Cockcroft-Gault formula, a commonly used surrogate marker for estimate of creatinine clearance (Cockcroft & Gault, 1976).

$$eC_{Cr} = \frac{(140 - \text{Age}) \times \text{Mass (in kilograms)} \times [0.85 \text{ if Female}]}{72 \times \text{Serum Creatinine (in mg/dL)}}$$

#### Viral Load Assessment

A viral load assessment, conducted as part of routine clinical care any time between Week 6 and Week 18, will be ascertained through medical record review and recorded.

#### Depression and Anxiety

The Hospital Anxiety and Depression Scale (Zigmond & Snaith, 1983), a 14-item self-report measure, will assess depression and anxiety symptoms at each visit. This scale correlates with clinical ratings of depression and anxiety (Zigmond & Snaith, 1983) and is used with individuals with HIV/AIDS (Savard et al., 1998). This measure may be used as a mediator and a covariate.

#### HAART Adherence

HAART adherence will be assessed with a self-report measure, the Adult AIDS Clinical Trials Group Adherence to Antiretrovirals Instrument (Chesney et al., 2000) (Pre-Quit, Weeks 5, 9, 12, 18, 24) and pharmacy refill data (Weeks 12 & 24), as we have done successfully with CFAR patients (Grossberg, Zhang, & Gross, 2004). In order to collect pharmacy refill data, the research staff will call the participant's pharmacy to obtain prescription refill dates for a specified antiretroviral medication (see Index Drug determination procedures). The refill date, number dispensed, dosage, and frequency will be collected. We will compute an adherence variable that consists of the percentage of doses taken over doses prescribed according to medical refill records (Gross et al., 2006). These data will consider all information on HAART use (e.g., type, dose).

**Index Drug:** The protease inhibitor (PI) or non-nucleoside reverse transcriptase inhibitor (NNRTI) will be the index drug of interest. For participants taking both a PI and NNRTI, the PI will be the index drug because studies to date that have assessed viral load change in relation to adherence have focused primarily on PIs. For participants taking two PIs including ritonavir, ritonavir will be the index drug.

Ritonavir is rarely used as a single PI and is therefore indicative of dual PI therapy. Dual PI regimens are used primarily in patients who have experienced treatment failures with other PIs. Therefore, participants on ritonavir plus a second PI (e.g., saquinavir or indinavir) are more alike than individuals on the second PI (e.g., saquinavir or indinavir) alone. Thus, assessing the ritonavir will be more relevant in this subgroup. If the participant is not on NNRTI or PI, the integrase strand transfer inhibitor (ISTI) will be the index drug. If the participant is not on NNRTI, PI or ISTI, the CCR5 antagonist (maraviroc) will be the index drug. In participants taking an abacavir-containing triple nucleoside

regimen, abacavir will be the index drug because it has the most antiviral activity of the nucleoside analogue reverse transcriptase inhibitors and is used in the place of a PI or NNRTI in this setting.

#### Nicotine Metabolic Rate (3-HC/cotinine ratio) and Genes related to Nicotine Dependence

Two baseline blood samples will be collected at Intake and analyzed for nicotine metabolites to determine rate of nicotine metabolism. Nicotine is metabolized to cotinine and then to 3-HC by the P450 (CYP) 2A6 enzyme (Nakajima et al., 1996). The 3-HC/cotinine ratio is a stable measure of the rate of nicotine metabolism, which influences response to nicotine dependence treatments (Lerman et al., 2006; Patterson, [name] et al., 2008). Variation in 3-HC/cotinine and other genetic polymorphisms in nicotine metabolizing enzymes (CYP2A6) and in drug targets (CHRNA4, CHRN2, etc.) will also be explored for associations with therapeutic response to treatment. The biosamples of individuals who complete the Pre-Quit visit will be sent to the laboratory of [name] at the University of Toronto for analysis. These analyses will be exploratory.

#### Bipolar Disorder Symptoms

If a diagnosis of bipolar disorder is self-reported at Initial Eligibility Screen or Intake, or revealed via the MINI at Intake, the Montgomery-Asberg Depression Rating Scale (MADRS), Young Mania Rating Scale (YMRS), and a Bipolar Disorder Additional Screener will be completed to evaluate and monitor the presence and severity of bipolar disorder symptoms.

#### Mediating Variables.

##### Mood: Positive and Negative Affect

The Positive and Negative Affect Schedule (PANAS; Watson et al., 1988), a 20-item self-report measure, assesses positive (PA; 10 items, e.g., enthusiastic) and negative (NA; 10 items, e.g., distressed) affect. The inclusion of PA is a strength since it is less frequently examined as a mediator of smoking cessation. The PANAS subscales are internally consistent ( $\alpha = .84\text{--}.91$ ) and exhibit good validity (Watson et al., 1988). The depression and anxiety scales described above will be mediators as well. The PANAS will be administered at Pre-Quit, Target Quit Day, and Weeks 3, 7, and 12.

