## **2. Statistical Analysis**

### **Power**

Power is provided for the primary aims since the exploratory aim is hypothesis generating. Power calculations were all approximated as t- or z-tests (2-sided,  $\alpha = .05$ ), and conducted using PASS Software (Power and Sample Size, NCSS Software, Kaysville, UT).

Aim 1: The primary analysis is a comparison in week 12 and 24 cotinine-confirmed 7-day point prevalence quit rates between placebo and varenicline. For the week 12 comparison, we based our sample size selection on the expectation that quit rates in the placebo and varenicline arms would approximate those reported in past varenicline trials with the general population of smokers (i.e., placebo = 21.2%; varenicline = 50.3%; Gonzales et al., 2006). With a sample of 310, we have >90% power to detect a significant effect between our treatment arm. Notably, we have 80% to detect a difference in week 12 quit rates if the difference between treatment arms is as small as 15%, not 29% as found in Gonzales et al. (2006), since the effect for varenicline may be smaller in this sub-group of smokers. For the week 24 comparison, we based our sample size on the expectation that the quit rate in the placebo arm would be 14.5%, vs. 33.5% for varenicline (Gonzales et al., 2006). In this case, we have 85% power to detect a significant difference between treatment arms. However, we have 80% power to detect a difference between treatment arms if the treatment arm difference is only 15%, not the 19% reported in Gonzales et al. (2006), since the effect for varenicline may be smaller in this sub-group of smokers. Even though it may appear that we are over-powered for Aim 1, we require the proposed sample to conduct the non-inferiority analyses for Aim 2.

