Aim 2: The analyses are a comparison in week 12 and 24 differences in QOL and severe side effects. For QOL, the overall scale mean among HIV/AIDS patients is 58.3 (SD = 24.5, Range 14-100; Holmes & Shea, 1998). We have 80% power to detect a mean difference of 7.8 at any time-point between the treatment arms with the proposed sample of 310. For side effects, the analyses will involve a test of non-inferiority since we cannot use standard statistical tests and conclude that a non-significant comparison shows that the drug is safe (i.e., "the absence of evidence is not evidence of absence"). In our past study with varenicline, 61% of participants on varenicline reported no severe side effects, vs. 76% of participants on placebo, a 15% difference (Patterson et al., 2009). With the present sample size, we will have 80% power to detect similar equivalence between treatment arms in terms of the frequency of severe side effects over the course of the 12-week treatment, given that side effects are actually non-significantly different across the treatment arms.

Aim 3: The analyses will assess changes in affect and cognitive function as mediators of treatment arm effects at week 12 and 24. These measures are continuous difference scores. Our sample of 310 is well above the minimum sample of 200 recommended for models of this size (Haduk, 1987; Boosma & Gabrielli, 1985). The mediation hypothesis will examine the proportion of treatment effect explained (Lin et al., 1997; Vittinghoff et al., 2009), and will test each mediation hypothesis with a z-score generated using the delta method. Our sample of 310 gives us 80% power to observe small effects in a 1-sample test ( $\delta=0.20$ ) when testing at  $\alpha=0.05$ . There are four proposed mediating pathways (2 measures of affect and cognition, respectively) between treatment and outcome, so our type-1 error will be corrected to 0.0125. Our sample of 310 gives us 80% power to detect small to medium effects ( $\delta=0.19$ ) for changes in the proposed mediators, which we have seen in previous trials (Patterson et al., 2009; [name] et al., 2010a).

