**Aim 2: Assess effects of varenicline therapy on QOL and side effects.** Repeated-measures MANOVA will examine differences across treatment arms in QOL (total scale score and subscale scores) over the trial. Participant covariates will be included, such as medical treatment history. In addition, we will compare treatment arms in terms of the frequency of severe side effects (*individual, including cardiovascular side effects, and total*). Using logistic regression, we will test against the lower boundary on percent reporting only mild-moderate (i.e., < severe) side effects. The hypothesis test for equivalence is a test of whether the OR is out of the prescribed range for the difference between the treatment arms. This approach provides a more valid test of the potential safety of varenicline for individuals with HIV/AIDS vs. a simple comparison of mean responses on a side effects measure. *We will also examine if participants on tenofovir (vs. other HAART) experience a greater frequency or more severe varenicline side effects by including type of HAART as a covariate in these analyses and, if so, we can explore if this relationship is mediated by varenicline plasma levels using a regression-based path model. Lastly, we will also examine if the frequency of cardiovascular side effects is different between treatment arms while considering if participants are currently taking HAART or not by including a covariate for current HAART use in the logistic regression models of side effects.*

**Aim 3: Assess changes in affect and cognitive impairment as mediators of varenicline therapy's effect on quit rates.** We will use a regression-based path model approach to examine mediation of treatment effects based on MacKinnon et al. (2007). All variables will be standardized for the analyses. Candidate mediators include positive and negative affect and two cognitive performance task measures. Suspected mediators will be entered as standardized pre-post differences, continuously distributed and treated as normal in linear regression. The effects of treatment arm on mediators, and of mediators on outcome, will be assessed using linear regression and standardized variables. We will focus on changes in

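### The Aim 3 mediation alpha of 0.0125 counts four tests, but the plan examines two outcome weeks and is inconsistent on whether depression and anxiety are further mediators

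*Combined protocol and SAP*

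**What the plan says.** Three things have to be read together.

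**The correction.** Under Statistical Analysis, Power, Aim 3, the plan counts its tests: "There are four proposed mediating pathways (2 measures of affect and cognition, respectively) between treatment and outcome". It derives its threshold from that count: "so our type-1 error will be corrected to 0.0125". At that level the section claims "Our sample of 310 gives us 80% power to detect small to medium effects", with delta = 0.19. The Aim 3 paragraph under Data Analysis gives the same set: "Candidate mediators include positive and negative affect and two cognitive performance task measures". Each pathway is tested with a z-test on the product of its coefficients, with a delta-method standard error.

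**The outcome times.** The same Power paragraph opens: "The analyses will assess changes in affect and cognitive function as mediators of treatment arm effects at week 12 and 24". The Outcome Assessments section makes confirmed 7-day abstinence at Weeks 12 and 24 the primary outcome for Aim 3 as well as Aim 1. Neither place pools the two weeks for mediation, ranks them or adjusts for having two.

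**The mediators.** Under Mediating Variables, the section on positive and negative affect adds: "The depression and anxiety scales described above will be mediators as well". The HADS is introduced more cautiously under Screening/Covariate Measures, Depression and Anxiety: "This measure may be used as a mediator and a covariate". Neither sentence calls these pathways exploratory, a label that the protocol does use elsewhere (for the genetic and moderator analyses).

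**The concern.** By adopting a Bonferroni threshold, the sponsor chose to hold the Aim 3 family-wise error at 5%. That control is only as good as the count behind it, and the count covers mediators at a single time. If mediation can be claimed at either week, the four listed mediators already give eight tests. If the depression and anxiety scales stand on the same footing, there are twelve.

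At stake is how an Aim 3 result may be reported. A pathway reaching p < 0.0125 at either week, for any of four or six mediators, could be presented as significant after correction when the correction did not cover that set. The power statement is tied to the same count, so a larger divisor changes the detectable effect. The efficacy and safety conclusions of Aims 1 and 2 do not depend on this.

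**Working it through.** **Inputs.** Overall alpha 0.05, two-sided ("Power calculations were all approximated as t- or z-tests (2-sided"); N = 310, 80% power, delta = 0.19 and per-test alpha 0.0125 (Power, Aim 3); four mediators (Power and Data Analysis) or six with the depression and anxiety scales; two outcome weeks.

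**1. Reproduce the plan's figures.** 0.05/4 = 0.0125, an exact match. For a one-sample two-sided z-test, detectable delta = (z for alpha + z for power)/√N = (2.498 + 0.842)/17.607 = 0.190, and power at delta 0.19 is 80.2%. The plan's arithmetic is right for four tests. What is open is the number of tests.

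**2. Count the tests.**
- 4 mediators × 1 week = 4
- 4 mediators × 2 weeks = 8
- 6 mediators × 2 weeks = 12

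Withdrawal and urges, which Table 2 also lists under mediating variables, are not counted. Nor are the later mediator changes (Weeks 5, 7 and 9) that the plan says can be examined.

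**3. Family-wise error at 0.0125 per test.** Upper bound k × 0.0125; if the tests are independent and of exact size, 1 − (1 − 0.0125)^k.

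| Tests (k) | Upper bound | Independent |
|---|---|---|
| 4 | 5.0% | 4.9% |
| 8 | 10.0% | 9.6% |
| 12 | 15.0% | 14.0% |

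With assumed correlations of 0.3-0.5 between mediators and 0.5-0.8 between weeks, still treating each test as having exact size 0.0125, simulation gives about 7-9% for 8 tests and 10-12.5% for 12.

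**4. Allow for the test actually planned.** A product-of-coefficients z-test with a delta-method standard error rejects less often than its nominal level when either path is weak. Simulation: 200,000 draws; path statistics treated as normal, with a standardised path of size b centred at b√310; critical value 2.498; the same treatment-to-mediator estimate used for both weeks, because the plan focuses on change to Week 3; assumed correlation 0.6 between weeks on the mediator-to-outcome path. The first three rows cover mediator correlations of 0 to 0.4 and either path being the null one.

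| True state | 8 tests | 12 tests |
|---|---|---|
| Both paths null | about 0% | about 0% |
| One null, other 0.2 | 0.6-0.9% | 0.9-1.3% |
| One null, other 0.3 | 2-3% | 3-5% |
| Mediator-to-outcome null, treatment-to-mediator 0.5-1.0 (mediator correlation 0.4) | 6-8% | 9-11% |

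In the last row, uncorrelated mediators give slightly higher figures. When the treatment-to-mediator path is the null one, the eight tests share only four such estimates, so their error stays at or below about 4 × 0.0125 = 5% however strong the other path is.

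**5. Cost of a matching divisor.**

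| Tests | Alpha per test | Detectable delta at 80% power, N = 310 | Power at delta 0.19 |
|---|---|---|---|
| 4 | 0.0125 | 0.190 | 80.2% |
| 8 | 0.00625 | (2.734 + 0.842)/17.607 = 0.203 | 72.9% |
| 12 | 0.0042 | (2.865 + 0.842)/17.607 = 0.210 | 68.4% |

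**The case against.** The strongest reply has three parts.

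**Mediators.** A reader might infer from the affect section that the plan has six confirmatory mediators and so twelve tests. The documents do not settle that. Both statistical sections give four and tie the correction to those four, and the HADS description is optional. This stands: the twelve-test count is a possible reading of conflicting passages. It does not rescue the divisor, because the two outcome weeks alone make eight tests. The wording of the Data Analysis list is also not strictly exhaustive.

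**Size.** A reader might also take 10% or 15% as the error rate the trial will have. The planned test does not support this. For paths of about 0.2, the size the plan powers for, the simulated family-wise error is near 1%. This stands too, and it limits the point. The excess over 5% needs a strong treatment effect on the mediators combined with no mediator effect on abstinence. The control in the other cases is a by-product of the test's conservatism, and the plan does not rely on that argument. Its own correction is a count-based one and should use the right count.

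**Outcome weeks.** Week 24 might be seen as a second look at the same pathway, or the two weeks might be meant to be pooled, as in the Aim 1 mixed model. Either would leave four tests. The Aim 3 text states neither, and it does not require mediation to hold at both weeks.

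**Conclusion.** The point holds in a limited form. The threshold of 0.0125 is correctly calculated for four pathways at one outcome time. It does not match an aim that names two outcome weeks, and the documents disagree on whether depression and anxiety are further mediators. The guaranteed ceiling on family-wise error is 10% for eight tests and 15% for twelve, against an intended 5%. The actual error is likely to be below 5% unless one path is strong, when it reaches about 6-8% for eight tests and 9-11% for twelve. Those simulated figures rest on the assumed correlations and normal path statistics described above; the ceilings do not.

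The eight-test count assumes that each week is tested separately and that either may support a claim, since the plan gives no other rule. Nothing in the documents shows that Week 24 in particular must give way: both weeks are primary for Aim 3, and which to keep is the sponsor's choice. The consequence is low, because only the mechanism claims are affected.

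**What to change.** First, reconcile the four places that define the mediators (the affect section, the HADS description, the Power section and the Data Analysis section) by labelling the depression and anxiety pathways exploratory in all of them.

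Second, state the confirmatory family with its outcome week or weeks, and make the divisor match. Either option works:

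- **Keep both weeks.** Four mediators × two weeks, tested at 0.05/8 = 0.00625 each, or by Holm over the eight tests at 0.05 overall. Restate the detectable delta as 0.203 in place of 0.19 (the Bonferroni figure).
- **Name one confirmatory week.** Four tests at 0.0125, with delta = 0.19 unchanged and the other week labelled exploratory.

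The cost is a sentence or two of text and no change to data collection. The first option gives a slightly larger detectable effect (power at 0.19 falls from 80.2% to 72.9%). The second gives up a confirmatory claim at one week. Under both, the depression and anxiety mediation results are hypothesis-generating.
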